171 Stage 1 and 2 fractures are considered stable and can be treated non-operatively. Stage 3 fractures are
 172 complete and traverse the entire course of the metaphysis, chondroepiphysis and the articular cartilage
 173 leaving the fragment without any attachment. These fractures can be undisplaced but are always
 174 considered unstable. Treatment controversy arises from the inability to distinguishing stage 1 and 2
 175 from stage 3 on plain radiographs.
 176

[figure not shown]

177
 178
 179

Figure 1 - Song classification.

180 Because of the risk of secondary displacement, operative treatment is often conducted with many
 181 surgeons choosing open reduction and fixation in all cases [19,20]. Operative fixation imposes the risk
 182 of minor complications such as superficial infection, ulcers and granulomas but also major complications
 183 such as deep infection, osteomyelitis, malunion, non-union, growth disturbance and osteonecrosis [21].
 184

185 MRI with specific cartilage sequences (figure 2) can clearly show the chondroepiphysis and studies
 186 have shown that MRI is capable of precisely showing the fracture pattern [2,3,5,22]. Using simple
 187 techniques and advances in technology to prepare the child, MRI has been shown to be feasible in
 188 younger children without sedation or anesthesia in whom this was previously thought necessary [23–
 189 30].
 190

191
 192
 193
 194

Figure 2 - MRI showing LHC. Left: Stage 1, confined to metaphysis. Center: Stage 2, fracture line stops in the chondroepiphysis. Right: Stage 3, traverses the joint cartilage.

195

196 5 Primary and secondary objectives

197 5.1 Primary objective

198

199 To describe the functional outcome two years after non-operative treatment of undisplaced and
200 minimally displaced LHCF in children.

201 5.2 Secondary objective(s)

202

- 203 • Describe the feasibility of performing a subacute MRI of the elbow in children with LHCF within 2-7
- 204 days after the injury without sedation or anesthesia
- 205 • Report MRI findings and classify fractures according to Song classification based on MRI
- 206 • Report the number and proportion of fractures that displace secondarily and their treatment
- 207 • Report final treatment; non-operative or operative
- 208 • Describe radiographic results and compare with MRI
- 209 • Report any early or late complications

210 5.3 Hypothesis

211

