 291 system. Parents are usually very keen to take their children for follow-up appointments making the risk
 292 of missing an appointment low. Any participants who miss an appointment will be contacted by phone to
 293 reschedule.

294

295 Table 1: Study schedule

296

Assessment parameters	Out-patient clinic visits and imaging procedures *										
	Visit 1**	Visit 2	Visit 3	Visit 4	Visit 5	Visit 6	Visit 7	Visit 8	Visit 9	Visit 10	
	Injury (day 0)	Screening	Information visit	Enrollment and consent	5 (± 3) days	12 (± 3) days	4 weeks	3 months	6 months	12 months	24 months
Eligibility	X										
Patient information		X									
Consent			X								
Demographics			X								
MRI				X							
If applicable - Control-MRI					(X)						
Cast removal***						X					
Radiographs and clinical exam					X	X	X	X	X	X	

297

298 * All FU visits with the defined time windows are calculated from the day of injury (i.e. day 0).

299 ** Telephone interview.

300 *** Casting may be prolonged two weeks in case of lack of callus formation at four weeks.

301

302 6.2.1 Visit 1: Screening (by phone)

- 303 • As described in section 6.1.4, the parents of potential study patients are informed about the study
304 over telephone by the PI.

305 6.2.2 Visit 2: Information visit

- 306 • All inclusion and exclusion criteria are checked to decide if the patient can participate in the study.
307 • Specific procedures for enrollment of pediatric patients are undertaken. A more detailed description
308 of the enrolment of participants and informed consent process is provided in section 6.1.4 and 10.
309 • Before any study-specific examinations are performed, the patient's parents give written informed
310 consent to participate in the study according to the CIP.

311 6.2.3 Visit 3: Enrolment, consent and preparation for MRI

- 312 • Obtain baseline demographics
313 • Book MRI
314 • Prepare child for MRI using the Child Centered Care model described in section 6.3
315 • Data verification and entry into the eCRF

316 6.2.4 Visit 4: MRI (5 (± 3) days)

- 317 • The MRI is performed according to the Child Centered Care model described in section 6.3
318 • Results of the MRI are given to the parents by phone
319 • Any necessary adjustments to the treatment plan is made
320 • Entry into the eCRF

321 6.2.5 ONLY if applicable: Control-MRI (12 (± 3) days)

- 322 • If an unstable Song stage 3 fracture is diagnosed based on the initial MRI an additional control MRI

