323 is performed during this visit
324 • Results of the MRI are given to the parents by phone
325 • Any necessary adjustments to the treatment plan is made
326 • Entry into the eCRF

327 6.2.6 Visit 5: Radiographs and clinical examination (12 (± 3) days)

- 328 • Plain radiographs of injured elbow without cast (AP, ML and IO)
329 • Clinical examination
330 – Cast condition
331 – Assessment of pain and use of pain medication
332 – Neurovascular status of the hand
333 • Entry into the eCRF

**334 6.2.7 Visit 6, 7, 8, 9 and 10: Radiographs and clinical examination (4 weeks and 3, 6, 12 and 24
335 months).**

- 336 • Plain radiographs of injured elbow without cast (AP, ML and IO)
337 • Clinical examination
338 – Assessment of pain and use of pain medication
339 – Neurovascular status of the hand
340 – Bilateral elbow assessment according to Mayo Elbow Performance Score (MEPS)
341 – Bilateral carrying angle of the elbow measured in degrees by goniometer
342 • Entry into the eCRF

343 **6.2.8 Unscheduled visits**

344 Unscheduled visits can take place at any time during the study if a need occurs or if the investigator
345 considers this to be appropriate for patient care. Information collected between study visits are to be
346 documented at the next regular study visit with the following exceptions:

- 347 • If a patient drops out of the study, a dropout form is completed at the time of dropout

348 **6.2.9 Premature study termination**

349 Patient participation in the study may end prematurely for one of the following reasons:

- 350 • Patient withdrew informed consent
- 351 • Protocol violation
- 352 • Investigator's discretion (e.g. patient noncompliance with CIP)
- 353 • Unknown/lost to FU

354

355 For each case of premature termination detailed information will be obtained explaining the
356 circumstances leading to the termination. This will be recorded on a dropout form in the eCRF.

357

358 If patients are withdrawn from the study, any collected data will be censored. Censoring allows this
359 collection of data to be accounted for in the analysis.

360 **6.3 Study treatments**

361

362 This study is not investigating any medical device. All devices in this study will be used per standard of
363 care at the participating institutions.

364 **6.3.1 Emergency treatment**

365 All patients who sustain a LHCF are initially treated in the ED with an above elbow splint. Parents and,

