429 Patient and parents are informed of the MRI findings and the following treatment (operative or non-
430 operative) by the PI.

431 **6.3.5 Operative treatment**

432 If the MRI cannot be completed for any reason, the images are insufficient in establishing fracture
433 pattern or if the MRI shows an unstable fracture which is displaced more than 2 mm, we will suggest
434 operative treatment with Kirschner wire fixation. Further participation in this project will be terminated.

435 **6.3.6 Non-operative treatment**

436 Patients with undisplaced and minimally displaced LHCF as seen on MRI will follow a non-operative
 437 treatment protocol (appendix 1). The treatment consists of an above elbow splint until radiographic
 438 union. Radiographic union usually occurs after four weeks; however, treatment will be continued until
 439 callus formation is seen at the cortex of the metaphysis.

440
 441 Fractures that are not complete (e.g., do not traverse both metaphysis, physis, epiphysis and joint
 442 cartilage) are considered stable. Complete fractures displaced <2 mm are considered unstable but still
 443 eligible for non-operative treatment. All patients will be seen for FU as outlined in section 6.2.

444
 445 Any patient with a fracture seen to displace more than 2 mm during FU will be suggested operative
 446 treatment.

447 **7 Definitions of outcome measures and study variables**

448 **7.1 Primary outcome**

449 **7.1.1 Mayo Elbow Performance Score (MEPS)**

450 MEPS consists of four domains; pain, elbow range of motion (ROM), stability and function [35]. We use
 451 a modified MEPS which omits the functional domain because it is not relevant in smaller children. The
 452 total score ranges from 0-100 with higher scores indicating better function (figure 5). If the total score
 453 ranges between 75 and 100, the result is good (satisfactory); 50–74, fair (acceptable); <50, poor
 454 (unsatisfactory) [36]. MEPS has been found to be accurate and reliable compared to other elbow
 455 scoring systems [37].

Criteria	No. of points
PAIN (max., 60 points)	
None	60
Mild to occasional, no medication	40
Moderate to occasional, activity limited, medication	20
Severe to incapacitating	0
MOTION (max. 30 points)	
Arc of extension/flexion:	
>90	30
60–89	20
30–59	10
<30	0
STABILITY (max., 10 points)	
Effect on function of the elbow	
None or mild (does not limit activity)	10
Moderate (impairs certain functions)	5
Severe (markedly limits activity)	0

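### Section 6.3.5 does not say whether its end-of-participation rule covers the control MRI; read literally, Song stage 3 children who fail non-operative treatment would leave before any MEPS is recorded

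*Protocol*

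**What the plan says.** Five parts of the protocol bear on a child who is already splinted and has a control MRI.

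- **6.3.5 Operative treatment.** Surgery is suggested if the MRI is not completed, if its images are too poor to settle the pattern, or, in the protocol's words, "pattern or if the MRI shows an unstable fracture which is displaced more than 2 mm, we will suggest" operative treatment. The closing sentence is "Further participation in this project will be terminated". The section speaks of *the MRI* and does not say which scan.
- **6.2.5 Control-MRI.** "If an unstable Song stage 3 fracture is diagnosed based on the initial MRI an additional control MRI" is done. The section then provides for adjusting the treatment plan and says nothing about participation. Its heading, "6.2.5 ONLY if applicable: Control-MRI (12 (± 3) days"), gives the same window as the radiograph visit, "6.2.6 Visit 5: Radiographs and clinical examination (12 (± 3) days").
- **6.3.6 Non-operative treatment.** "Any patient with a fracture seen to displace more than 2 mm during FU will be suggested operative" treatment. No imaging modality is named and no end of participation is stated. The same section says "All patients will be seen for FU as outlined in section 6.2".
- **6.2.9 Premature study termination.** The reasons are withdrawn consent, protocol violation, investigator's discretion (with noncompliance as the example) and loss to follow-up. Neither surgery nor an MRI finding is named.
- **8.3.1 Patient discontinuation.** Removal is limited to families who decline to take part. For drop-outs, the latest examination is carried forward.

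Among the secondary objectives, Section 5.2 includes "Report the number and proportion of fractures that displace secondarily and their treatment".

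**The concern.** Only children with a stage 3 fracture on the first MRI get a control MRI. Section 4.4 describes stage 3 as always unstable, and the hypothesis in Sections 5.3 and 8.1 expressly includes stage 3. A stage 3 child displaced by more than 2 mm on the control scan has started the study treatment and failed it.

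If 6.3.5 governs that scan, the child leaves the study because of the failure. If 6.3.6 governs, the child stays to 24 months. The protocol does not say which, so retention would be decided case by case once the failure is known. At stake are the 24-month MEPS and late complications of the very children who test the stage 3 part of the hypothesis. In a single-arm descriptive study there is no comparator to reveal such a loss.

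**Working it through.** **1. The two rules applied to the same child at about day 12.**

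| Control MRI result | 6.3.5, if it covers this scan | 6.3.6 |
|---|---|---|
| Displaced more than 2 mm | Surgery suggested; participation ends | Surgery suggested; no end of participation; follow-up per 6.2 |
| Not completed or unreadable, Visit 5 radiograph undisplaced | Surgery suggested; participation ends | Not triggered; splint and follow-up continue |

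In the first row the sections agree on treatment and differ on participation. In the second they differ on both, but only if 6.3.5 reaches the control scan.

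**2. Does the wording allow 6.3.5 to reach the control scan?** Yes. Section 6.2.5 writes *initial MRI* when it means the first scan, and uses plain *the MRI* for the control scan when results are phoned to the parents. Section 6.3.5 uses the plain form. It equally does not exclude 6.3.6: the control MRI lies in the Visit 5 window, and Section 11.4 lists MRI in unstable injuries beside the extra follow-ups as a guard against unnoticed displacement.

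**3. What would be lost.** Section 6.2.7 starts MEPS at Visit 6 (4 weeks). Visit 5 in Section 6.2.6 has none. A child who leaves around day 12 has no MEPS, so carrying the latest examination forward cannot supply one.

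**4. Size.** The protocol gives no figure for this loss, and N = 50 has no formula to reproduce. The percentages it quotes from the cited MRI series (Section 10) do reproduce: 17/25 = 68%, 6/25 = 24%, 23/25 = 92%.

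Inputs: N = 50 (6.1.4), taken as children going to a first MRI; scan completion 25/27, complete but minimally displaced 6/25, non-operative 23/25 (Section 10); secondary displacement 4% to more than 40%, expected close to 4% (11.3.1).

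- Completed first scans: 50 × 25/27 = 46.3
- Stage 3, minimally displaced: 46.3 × 6/25 = 11.1
- Non-operative cohort: 46.3 × 23/25 = 42.6
- Stage 3 children who displace: 11.1 × 0.04 = 0.4; 11.1 × 0.40 = 4.4
- Share of the non-operative cohort: 0.44/42.6 = 1.0%; 4.44/42.6 = 10.4%
- Chance of at least one among 11: 1 − 0.96^11 = 36%; 1 − 0.60^11 = 99.6%
- Incomplete control scans at the first-scan failure rate: 11.1 × 2/27 = 0.8, probably too high because these children have already completed one scan

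**5. Possible effect on the result (assumed outcome rates, not in the protocol).** Suppose 95% of children without displacement have a good MEPS and between 0% and 95% of those with displacement do. Leaving out every displaced stage 3 child raises the cohort's good-outcome rate by 0 to 0.010 × 95 = 1.0 point at 4%, and by 0 to 0.104 × 95 = 9.9 points at 40%.

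The counts and shifts at each rate are upper bounds, because only displacement seen on the control MRI could trigger 6.3.5.

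**The case against.** The best case for the protocol is that 6.3.5 is an allocation rule. Sections 6.3.1 to 6.3.6 run in order: emergency splint, MRI, result, then operative or non-operative treatment. The criterion about images too poor to settle the pattern fits a first scan; a child sent for a control MRI already has an established stage 3 pattern. The Definitions make the follow-up population the enrolled population, meaning consented patients who began treatment, and a splinted child at day 12 belongs to it. Section 5.2 asks for secondary displacements and final treatment to be reported. Section 19 follows enrolled patients to the last visit even if the study stops early. There is one centre, and the principal investigator reads the scans with senior radiologists, so varied interpretation is less likely than in a multicentre trial.

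Most of this stands. It makes the allocation reading the more coherent one, but 6.3.5 does not state it.

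Three stronger readings are tempting and are not supported:

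- A reader might infer that displacement seen on MRI is assigned to 6.3.5 and displacement seen on a radiograph to 6.3.6. Section 6.3.6 names no modality, so a control-MRI finding fits it too.
- A reader might infer that 6.3.5 is the only MRI-based rule available. Section 6.3.6 refers to Appendix 1 for the non-operative protocol; only its heading is available here, and it may address the control scan.
- A reader might infer that the sections give opposite orders for a displaced fracture. Both suggest surgery; they differ on participation.

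The investigator's discretion item in 6.2.9 could also be stretched to cover an MRI finding, although its example is noncompliance.

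**Conclusion.** The point holds as an ambiguity that should be closed: two overlapping rules with different consequences for participation, one of them at odds with 8.3.1 and not among the reasons named in 6.2.9. The protocol does not establish that stage 3 failures will be dropped. On a literal reading of 6.3.5 they would be, with no MEPS at all, and the loss would depend on treatment failure. That would favour the stage 3 result if failures do no better than the other children.

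The size is modest and uncertain: about 11 stage 3 children, of whom at most 0.4 to 4.4 are affected at 4% to 40%. At the investigators' expected 4% this is under half a child; near 40% it could be material. The estimate assumes that the cited series' mix applies here. It also applies displacement rates given for initially undisplaced fractures generally, not for stage 3, and the upper end of the quoted range is open.

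**What to change.** Change the wording in five places.

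1. In 6.3.5, limit the sentence that ends participation to the initial, treatment-allocating MRI.
2. In 6.2.5 and 6.3.6, state that a child who began non-operative treatment stays on the Visit 6 to 10 schedule and in the 24-month analysis, whatever the control MRI shows and whatever treatment follows. Count displacement found on that scan as secondary displacement.
3. Align 6.2.9 and 8.3.1 with this, so that the grounds for ending participation are the same throughout, including the initial-MRI termination if it is kept.

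Separately, the investigators must reconcile 6.2.5, 6.3.5 and 6.3.6, together with Appendix 1, on what a displaced or incomplete control MRI means for treatment. No clinical rule is proposed here.

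The cost is an amendment to the text and keeping visits already scheduled in Table 1 for a few more children.

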- 540 • Continuous variables will be summarized using the mean, standard deviation (SD), median, inter-
541 quartile range, and minimum and maximum values and, if appropriate, according to clinically relevant
542 categories.

543

544 In general, continuous variables with both baseline and FU measurements available will also be
545 summarized in terms of the individual patient-level changes between baseline and follow-up.

546

547 A p-value of <0.05 is regarded as being significant. Data will be analyzed using SPSS (SPSS, Chicago,
548 IL, USA).

549 8.3.1 Patient discontinuation

550

551 If a participant chooses to discontinue the follow-up examinations for any reason, the date and reason
552 for drop-out is recorded and the latest examination will be carried forward in the analysis. In case of
553 drop-out before the first follow-up visit the participant will be excluded from the analysis. Participants are
only removed from the study if they decline participation.

554 9 Bias

555

556 We strive to minimize bias in our study. Minimally displaced fractures of the elbow can go unnoticed and
557 be missed by our project. However, Danish parents are usually not withholding in taking an injured child
558 to the ED. A strict protocol for referrals for treatment are in place in Denmark. All eligible patients
559 referred to Herlev and Gentofte University Hospital will be asked to participate in the study. We
560 speculate that by enrolling 50 participants the cohort will be representative of the background
561 population. We speculate that these efforts will limit selection bias. Efforts described in the follow-up
562 section reduce the risk of loss to follow-up. Overall, we find a low risk of bias in our study for the chosen
study design and size.

563 10 Benefits

564 Classifying lateral condyle fractures and establishing whether they are stable or not is the key to
565 choosing the right treatment strategy. MRI is the only feasible image modality that can make that
566 distinction.

567
568 LHCF is currently a fracture that requires open surgery in most cases due to the radiographic inability to
569 distinguish stable injuries from unstable. This project seeks to use MRI without sedation or GA in order
570 to distinguish fracture patterns. MRI has been shown to be feasible in all age groups without the need
571 for sedation or GA [24].

572
573 Thévenin-Lemoine et.al. found that 25 of 27 children could successfully complete an MRI without

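### Section 8.3.1 lets a MEPS taken between 4 weeks and 12 months stand as the two-year primary result, and its removal rule contradicts 6.2.9 and 6.3.5

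*Protocol*

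**What the plan says.** The synopsis names MEPS two years after injury as the primary outcome, and 8.3 plans simple summary statistics for a single cohort.

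On incomplete follow-up, 8.3.1 makes three statements:
- Its trigger is "If a participant chooses to discontinue the follow-up examinations for any reason". The date and reason are then recorded and "the latest examination will be carried forward in the analysis".
- In case of "drop-out before the first follow-up visit the participant will be excluded from the analysis".
- Participants are "only removed from the study if they decline participation".

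Other sections bear on these statements:
- 6.2.7 lists MEPS at Visits 6 to 10 (4 weeks and 3, 6, 12 and 24 months). 6.2.6 does not list it at Visit 5 (day 12). Table 1 puts cast removal at the 4-week visit, and its footnote allows a further two weeks of casting.
- 6.2.9 gives four reasons for premature termination: withdrawn consent, protocol violation, investigator's discretion, and "Unknown/lost to FU". It adds: "If patients are withdrawn from the study, any collected data will be censored". The next sentence says that censoring lets these data be accounted for in the analysis.
- 6.3.5 ends participation when the MRI cannot be completed, is insufficient, or shows an unstable fracture displaced more than 2 mm.
- 6.2 regards the risk of a missed visit as low and relies on a telephone call to reschedule. No drop-out rate is given.

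**The concern.** A two-year summary should describe children at two years. Under 8.3.1 a child who leaves after the 4-week visit contributes a score taken as the cast comes off, and a child who leaves after the 12-month visit contributes one that is a year early. In a one-arm description there is no control group in which such an error could partly cancel.

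The protocol itself gives a reason why an early score may be too low: 11.1 lists joint stiffness as a risk of casting. The opposite error is also possible, if a child scores well early, leaves and then deteriorates.

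The second problem is who is counted. If declining is the only ground for removal, a child ended for a protocol violation, at the investigator's discretion or after the MRI has not been removed. Sections 6.2.9 and 6.3.5 say that these children's participation ends. The two-year denominator depends on which statement governs.

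**Working it through.** The protocol states no power, precision or drop-out figure, so there is nothing to reproduce. The sizes below are illustrations.

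**Inputs**
- Planned enrolment: 50 (6.1.4).
- Alternative base: section 10 describes a cited series of 27 children, of whom 25 completed MRI and 23 could be treated non-operatively. Assuming the same share here, 50 × 23/27 = 42.6, about 43.
- Loss: assumed 2 to 10 of 50 (4.0% to 20.0%), or 2 to 9 of 43 (4.7% to 20.9%).
- Scoring (7.1.1, Figure 5): pain 60/40/20/0, arc of motion 30/20/10/0, stability 10/5/0; 75 or more is 'good'.

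**What an early score can look like (stable elbow, 10 points)**
- No pain, arc 30–59: 60 + 10 + 10 = 80, good.
- No pain, arc below 30: 60 + 0 + 10 = 70, fair.
- Mild pain, arc above 90: 40 + 30 + 10 = 80, good.
- Mild pain, arc 60–89: 40 + 20 + 10 = 70, fair.

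In a pain-free, stable elbow, stiffness changes the category only if the arc is below 30 degrees. Mild pain with a moderately reduced arc also changes it.

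**Effect per carried child**
- Mean, score 30 points off (for example 70 carried, 100 true): 30/50 = 0.60; 30/43 = 0.70 points.
- Percentage 'good', one wrong category: 100/50 = 2.0; 100/43 = 2.3 percentage points.

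**Extreme case: every loss just after the 4-week visit, 70 carried, 100 true**
- Base 50: 30 × 2/50 = 1.20 to 30 × 10/50 = 6.00 points.
- Base 43: 30 × 2/43 = 1.40 to 30 × 9/43 = 6.28 points.

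**Milder case: losses spread evenly from day 12 to day 730 (718 days)**

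This takes Visit 5 as the first follow-up visit, which is an assumption because the synopsis also mentions a 1-week follow-up.

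| Last MEPS available | Days | Share of losses |
|---|---|---|
| none | 12–28 | 16/718 = 2.2% |
| 4 weeks | 28–91 | 63/718 = 8.8% |
| 3 months | 91–183 | 92/718 = 12.8% |
| 6 months | 183–365 | 182/718 = 25.3% |
| 12 months | 365–730 | 365/718 = 50.8% |

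If only the 4-week scores are wrong, the mean falls by 1.20 × 0.088 = 0.11 to 6.28 × 0.088 = 0.55 points. Children with no MEPS to carry number 2 × 0.022 = 0.04 to 10 × 0.022 = 0.22, a fraction of one child.

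**The removal rule against the other sections**
- 8.3.1: removal only on declining.
- 6.2.9: protocol violation and investigator's discretion also end participation, and neither is a refusal by the family.
- 6.3.5: certain MRI results end participation, again without refusal. At the rate in the cited series (2 not scanned, 2 displaced) this would be 50 × 4/27 = 7.4 children.

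These statements cannot all hold. The Definitions equate the follow-up population with those enrolled (consented and treatment commenced), which does not say who is counted at two years.

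**The case against.** The strongest reply is that little turns on this. The protocol expects few missed visits, the analysis is descriptive, and evenly spread losses move the mean by well under one point. Dates and reasons for drop-out are recorded, STROBE reporting is promised, and 8.3 can be read as summarising the observed 24-month values too. Displays and sensitivity analyses often belong in an analysis plan, which is not available here. All of this stands as to size and presentation. It does not change the fact that the protocol itself fixes carry-forward, or that its sections disagree on removal.

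Several stronger readings are tempting, and the protocol does not support them:
- *Carry-forward flatters the treatment by hiding late complications.* Section 4.3 does describe complications that appear years later, but after neglected, displaced fractures. The nerve palsy and angular deformity it names are not domains of the modified MEPS. Upward error is possible but not well documented here.
- *Loss to follow-up has no rule.* The trigger is worded as a choice, but it also says for any reason, and 6.2.9 records loss to follow-up on a dropout form. It is plausibly covered.
- *Section 6.2.9 discards the data of withdrawn children.* Its next sentence states the opposite intent. Censoring is the wrong term for a score summarised at a fixed time, but this is a matter of wording.
- *The roughly 7 children ended under 6.3.5 distort the primary result.* They fall outside the non-operative primary objective. That conflict concerns who is counted, not carry-forward.
- *Carry-forward puts up to 20 percentage points of 'good' in doubt.* The share of children missing (2/50 = 4% to 9/43 = 20.9%) is the uncertainty that any missing data create, whichever method is used.

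**Conclusion.** The point holds and should be fixed, although its expected effect is small. As written, 8.3.1 allows a MEPS from 4 weeks to 12 months to be reported as the two-year primary result. The best-documented direction is downward, which would work against the study's own hypothesis; the reverse cannot be excluded. Each carried score 30 points off costs 0.6 to 0.7 points of the mean, and each wrong category 2.0 to 2.3 percentage points of 'good'. Larger totals, up to about 6 points, need both heavy loss and losses concentrated just after cast removal, and nothing in the protocol suggests either. The loss rates, the 30-point error and the base of 43 are assumptions of this review.

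The contradiction between 8.3.1 and sections 6.2.9 and 6.3.5 rests on the text alone and needs no assumption. The child who leaves between Visits 5 and 6 and the 'censored' wording are minor drafting points, not separate errors.

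**What to change.** - Make MEPS observed at 24 months the primary summary, with the numbers observed and missing.
- For the proportion 'good', add two bounds: all missing children counted as good, and all counted as not good.
- Keep carry-forward only as a sensitivity analysis in children with at least one MEPS, showing the visit each carried score came from. This also disposes of the child with no MEPS.
- Apply the same rule to every missing 24-month MEPS, whatever the reason, including loss to follow-up and a missed final visit.
- Reconcile the reasons for ending participation in 6.2.9, 6.3.5 and 8.3.1, and state for each whether the child is in the two-year denominator. No view is taken here on which reasons should apply.
- In the same edit, replace the 'censored' wording of 6.2.9 with its stated intent: data collected up to withdrawal are used, in the summaries of the visits attended.

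The cost is protocol wording and two extra percentages. The primary summary would hold somewhat fewer children: under the assumed loss, 50 − 10 = 40 to 50 − 2 = 48 of 50, or 43 − 9 = 34 to 43 − 2 = 41 of 43. An observed-only mean can be biased if loss is related to outcome. The bounds address this for the proportion 'good' but not for the mean, and the report should say so.
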